3.1 General Design

The cardiovascular effects of Adderall, prescription medication often abused by students for non-medical purposes, are not well understood. This is a pilot study to investigate the cardiovascular and metabolic response to taking an oral dose of Adderall (25 mg) by healthy adults. Subjects will be studied using a randomized, double-blind, placebo-controlled, crossover design with two separate experimental sessions: Adderall and placebo pill; studies will be performed on 2 separate study days, each study lasting from 6-8 hours.

[figure not shown]
Active drug: Oral Generic Adderall: total of 25 mg dose. This dose will be compounded by Pharmacy. The compounded dose will contain: [dextroamphetamine sulfate 6.25 mg, dextroamphetamine saccharate 6.25 mg, amphetamine aspartate monohydrate 6.25 mg, amphetamine sulfate 6.25 mg (equivalent to amphetamine base 15.73 mg)].

Placebo drug: Placebo designed by CRTU Research Pharmacist team

Adderall and placebo drug will be prepared by research pharmacists in similar capsule form. Placebo pill is carefully designed by our team of CRTU Research Pharmacists to match the prescription medication, Adderall. Both drugs will be given in an identical manner so that participants and study investigators are not aware of which drug is being administered. Subjects will remain unaware of the nature of the drug administered on each study day throughout the study. Each experimental session (Adderall and placebo pill) will be conducted using the same protocol, in a random order.

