Study participants will be recruited and offered participation in this trial as described in other sections of this protocol. Interested qualified participants will be consented. The study will be performed at St Marys CRTU on two separate days minimum 5 days apart. Participants will be consented upon arrival to the CRTU and will be consented by the Research Staff. The start time of the studies will be the same. Participants will be fasting 4 hours prior to the study and will be asked to abstain from all stimulants, including caffeine and alcohol for at least 24 hours prior to initiation of this study. When presenting to the CRTU on the first day of the study, participant's height and weight will be obtained by the CRTU staff. On each study day, CRTU personnel will perform urine pregnancy test if needed. If positive pregnancy test, participant will not be able to participate in the study. The research staff will obtain waist and hip and bioimpedance measurements (described below); the participant, together with the research staff, will fill out several questionnaires regarding cardiovascular health and dietary habits (attached with application). Subsequently, the participants will take part in research studies as outlined below. Baseline measurements will be obtained at rest. After the end of baseline recordings, the subjects will be given 25 mg oral dose of Adderall vs placebo pill. The second set of measurements will be obtained starting 3 hours after taking the pill, using similar protocol as at baseline.

We expect to enroll approximately 25 healthy subjects.

Schematic diagram (flowchart) of study events:

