5.9.4 Return or Destruction of Study Drug

Study drug will be supplied by the Mayo Clinic pharmacy on a one-to-one basis, rather than batches. In this respect we do not anticipate to have drugs remaining or drugs to return. At the completion of the study, there will be a final reconciliation of drug provided by the Mayo Clinic Pharmacy, drug dispensed, drug returns, and drug remaining. This reconciliation will be logged on the drug reconciliation form, signed and dated. Any discrepancies noted will be documented and investigated, prior to return or destruction of unused study drug. Drug destroyed on site will be documented in the study files.

6 Study Procedures

6.1 Visit 1

Two CRTU visits - minimum 5 days apart, maximum 3 months apart.

CRTU Day # 1

1. Subjects report to SMH CRTU at the already pre-scheduled appointment time. Participants should not eat at least 4 hours prior to coming to CRTU. Participant is reminded to avoid all stimulants including caffeine and alcohol 24 hours prior to the study.
2. CRTU personnel informs study personnel when the subject arrives at the CRTU.
3. Study personnel explain the research study to the participant and obtain written informed consent.
4. CRTU personnel will obtain height and weight of the participant.
5. CRTU personnel performs urine pregnancy test as needed (Urine collection #1). If the participant is pregnant, then the participant is unable to participate in the study, and will receive \$25.00 for their time. In all participants at least 100 ml of urine may be collected for future biomarker analysis at baseline
6. Study personnel verbally ask and record the responses to Cardiovascular Research Data Sheet including anthropometrics and bioimpedance measurements.

7. Participant will be asked to fill out the following questionnaires on a Mayo laptop or on paper. Some of these questionnaires may be administered more than once: Stimulant Intake Questionnaire, Berlin Questionnaire, Breakfast Questionnaire, Food Scale, Food Intake Questionnaire, Adult ADHD Self Report Checklist, Symptoms Questionnaire, Sleepiness Scale.
8. CRTU Staff will insert peripheral intravenous line into the forearm and blood draw #1 will be obtained after at least 30 minutes of supine resting.
9. Study personnel will obtain BP and HR measurements in supine position. Measurements will be taken every 1-3 minutes throughout the study.
10. Study personnel will be obtaining 12-lead ECG recording throughout the study.

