7.1 Sample Size Determination

Anticipating to study 30 subjects, we will have 80% power to detect a significant increase in the blood parameters (i.e. BP, HR etc.) for the study drug as compared to the placebo drug, with a 2-sided significance level of 0.05. Specifically, we are powered to detect an effect size of 0.80, which is a difference in the means between the different types of drugs (study vs. placebo) that is 80% of the standard deviation. For example, we are powered to detect an increase of 5% in the blood parameters for the study drug vs. only a 1% increase for the placebo drug (4% difference), assuming a standard deviation of 5% (effect size = 0.80).

Data Analysis Plan: Plan is to analyze data using two-way analysis of variance (ANOVA) for repeated-measures with time (before vs after drug intake) as the within factor and group (study drug vs placebo drug) as the between factor. The key variable will be the group-by-time interaction. Differences in hemodynamics (BP, HR) before and after consumption of a drug will be determined by repeated measures ANOVA. Student *t* test (paired or unpaired) will be used for between group comparisons with respect to change in given variable. $P < 0.05$ will be considered statistically significant. Data will be expressed as mean \pm SEM.

Endpoints:

Primary Endpoint:

- 1) Determine the hemodynamic changes (magnitude of BP and HR response) in healthy adults after taking one dose of prescription medication Adderall 25 mg orally, one time, and compare these responses to those after a placebo pill

Secondary Endpoint:

- 1) Determine ECG changes and incidence of arrhythmias after consumption of Adderall compared to baseline ECG
- 2) Determine if consumption of a dose of Adderall is associated with altered neurohormonal and cardiovascular activation, assessed by measurements of biomarkers, such as catecholamines before and after Adderall/placebo intake
- 3) Determine if taking Adderall induces orthostatic changes
- 4) Assess baroreflex sensitivity (paced breathing) before and after Adderall vs placebo intake
- 5) Determine the effect of Adderall on cardiovascular hemodynamics during stress conditions including mental stress (arrhythmics), physical stress (sustained hand grip) and pain stress (cold pressor stress) as compared to measurements at rest
- 6) Determine the changes in heart function and brachial artery reactivity after Adderall intake using an ultrasound

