7.2 Statistical Methods

Descriptive Statistics

Univariate descriptive statistics and frequency distributions will be calculated, as appropriate for all variables. Baseline values for demographic, clinical, and outcome variables (primary and secondary) will be tabulated for both groups (i.e., study drug vs placebo drug). Data will be inspected before analysis for the need of transformations to reduce the possible impact of outliers in skewed distributions, and transformed accordingly. Distributions across subgroups used in randomization will also be compared to assess whether the randomization was successful in equalizing distributions of these prognostic variables across treatment groups. Putative prognostic variables that will be investigated through these descriptive analyses include variables such as BP, HR, age, gender, BMI, baroreflex sensitivity, catecholamine responses.

Handling of Missing Data

We expect missing data to be minimal. However, some subjects may drop out from the two study day protocol. The two-day longitudinal model is flexible to allow available data to be analyzed, for instance, if a subject completes the first study day, but not second study day. These models assume ignorable (MCAR/MAR) missingness. Sensitivity analyses may be performed to assess the robustness of these assumptions.

Multiplicity

There is no need to account for multiple comparisons in this study. With only 30 subjects, no correction for multiple comparisons using Bonferroni or Tukey's procedure will be necessary.

Primary Hypothesis: We hypothesize that BP and HR increase after intake of study drug compared to placebo.

Data will be analyzed using two-way analysis of variance (ANOVA) for repeated-measures with time (before vs after drug intake) as the within factor and group (study drug vs placebo drug) as the between factor. The key variable will be the group-by-time interaction. Differences in hemodynamics before and after consumption of a drug will be determined by repeated measures ANOVA. Student *t* test (paired or unpaired) will be used for between group comparisons with respect to change in given variable. $P < 0.05$ will be considered statistically significant. Data will be expressed as mean \pm SEM.

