7.3 Subject Population(s) for Analysis

All-randomized population: Any subject randomized into the study.

8 Safety and Adverse Events

The overall study risk for this protocol is considered greater than minimal risk.

Consent: Consent will be obtained before initiating study specific procedures. A quiet, comfortable, and private setting for the informed consent process will be provided. The consent process will be explained to the subject, time will be provided to consider all options and when possible the subject will be provided a copy of the consent form well in advance for review at

home. Study staff will consider the subject's likely reading abilities and provide an impartial witness in the informed consent process if necessary. All questions will be answered. Coercion or other undue influences will be avoided through the use of a quiet, comfortable, and private setting away from areas involved in direct clinical practice will be used for the informed consent process. The subject will be told that informed consent can be revisited at any time and consent can be withdrawn at any time without affecting the subject's medical care. The informed consent process will continue throughout the subject's participation in the study and consent will be informally verified on a continuing basis. Significant new information will be given to the subject as it is available.

Safety: While the measurements and interventions proposed in these studies are used frequently and often on a routine basis in our laboratory, there are some risks to some of the measurements and interventions which will be described below:

- The major risk is that of possible side effects of Adderall. The side effects are outlined in the prior sections of this document. As with any medication, allergic reactions are also a possibility. We will enroll only healthy young subjects. This risk potentially induced by Adderall will be minimized by administering short acting form of Adderall and only one time dose. In the event that subjects develop sustained side effects such as elevated BP, elevated HR or other form of arrhythmia that may acutely compromised subject's health, emergent care will be provided by the medical staff.
- To control for behavioral risks, subjects with a history of psychiatric disorders will be excluded from participation.

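### Crossover BP and HR are to be tested with drug as a between factor and pairing left open: name one within-subject model, and reconcile the comparators of secondary endpoints 1 and 6

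*Combined protocol and SAP*

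**What the plan says.** Section 3.1 describes a "crossover design with two separate experimental sessions". Section 5.3 has each subject complete two study days, and section 6.2 gives on day 2 whichever drug was not given on day 1.

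The analysis plan in section 7.1, repeated in section 7.2 for the primary and first secondary hypotheses, takes time (before, after) as the within factor and "group (study drug vs placebo drug) as the between factor. The key variable will be the group-by-time interaction". It adds that a Student t "test (paired or unpaired) will be used for between group comparisons with respect to change in given variable". No subject, period or sequence term is named.

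Under missing data, section 7.2 says "The two-day longitudinal model is flexible to allow available data to be analyzed", but that model is not defined. Section 7.3 gives one population: "All-randomized population: Any subject randomized into the study".

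Pre-dose values exist on both days. Before dosing, section 6.1 (step 9) states "Study personnel will obtain BP and HR measurements in supine position", and section 6.2 (step 7) repeats it.

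Secondary endpoint 1 reads "Determine ECG changes and incidence of arrhythmias after consumption of Adderall compared to baseline ECG", whereas Secondary Hypothesis 1 in section 7.2 compares ECG findings with placebo. Secondary endpoint 6 concerns changes in heart function by ultrasound. The visit steps list a heart ultrasound only after dosing, and as optional.

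**The concern.** A between factor is right for parallel groups. Here the same 30 people supply both sets of changes, so the error term must allow for their being the same people. The plan neither fixes that nor chooses between the two t tests, so the primary result could depend on a choice made after the data are seen. If the literal reading is used, the stated 5% level does not hold and the main benefit of a crossover may be lost.

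The two secondary endpoints have a related weakness. As worded, endpoint 1 contrasts two unlike stretches of the Adderall day instead of the Adderall and placebo days. Endpoint 6 asks for a change whose starting value does not appear in the visit steps.

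**Working it through.** **1. The plan's own figure.** Section 7.1 gives 30 subjects, two-sided 0.05, a 4% difference and a 5% SD, so d = 4/5 = 0.80, with 80% power.

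- Two independent groups of 25: 80.7% (normal), 79.1% (t).
- Two independent groups of 30: 87.3%, 86.1%.
- Two independent groups of 15: 59.1%, 56.2%.
- 30 pairs, 5% taken as the SD of the within-subject difference: 98.8%.

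Of these, only two independent groups of 25 come close to 80%. If 5% is instead the SD of one day's change, and ρ is the correlation of a subject's two changes, the paired effect size is 0.80/√(2(1−ρ)). At ρ = 0, 0.3 and 0.5, paired power is 85.0%, 94.7% and 98.8% with 30 subjects. With the 25 of section 3.1 ("We expect to enroll approximately 25 healthy subjects") it is 77.5%, 90.0% and 97.0%.

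**2. The literal test.** With two time points, the group-by-time interaction with drug as a between factor is the unpaired t test on change. It takes the variance of the mean difference as 2σ²/n, whereas the crossover gives 2σ²(1−ρ)/n. Simulation with 30 subjects and assumed ρ (effects in SDs of one day's change):

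| ρ | Level, unpaired | Level, paired | Power at 0.5 SD, unpaired / paired | Power at 0.8 SD, unpaired / paired |
|---|---|---|---|---|
| 0 | 5% | 5% | 48% / 47% | 86% / 85% |
| 0.3 | about 2% | 5% | 48% / 61% | 90% / 95% |
| 0.5 | 0.7%-0.8% | 5% | 47% / 76% | 93% / 99% |

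At ρ = −0.3 the unpaired level would be 8.2%-8.4%.

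**3. Paired change against baseline adjustment.** Let r be the correlation between the pre-dose and post-dose between-day differences, each with variance v. The change contrast has variance 2(1−r)v and the adjusted contrast (1−r²)v, so the ratio is 2/(1+r).

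First assume one between-day correlation rb for every cross-day pair, and same-day correlation rw. Then r = (rw−rb)/(1−rb). At rw = 0.7 and rb = 0.5, r = 0.2/0.5 = 0.4 and the ratio is 2/1.4 = 1.43. Where paired change has 80% power with 30 subjects, adjusted power by simulation (rw/rb) is about:

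- 82%-84% at 0.9/0.4
- 86%-87% at 0.8/0.4
- 91% at 0.7/0.5
- 97% at 0.6/0.6

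This set-up makes the covariance of the two changes proportional to rb − rb − rb + rb = 0. When the changes are instead correlated 0.2-0.5, the settings examined give about 81%-90%: for example, 84% at 0.7/0.5 and 81.5% at 0.8/0.4, both at correlation 0.5. The simulated level of the mixed model was 4.6%-5.9%.

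**4. Secondary endpoint 1.** In the visit steps the three stress tests come only after dosing. Section 8.1 expects about 4 hours after dosing. Section 3.1 gives a session of 6-8 hours, leaving 2-4 hours before dosing, not all with ECG running. The post-dose recording therefore differs in content and may be longer.

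As an illustration, assume a constant 0.1 arrhythmias per hour, 1.5 h before and 4 h after dosing, and no drug effect. The chance of at least one is 1−e^(−0.15) = 14% before and 1−e^(−0.4) = 33% after. A within-Adderall before/after t test is then positive in 38% of simulated trials. At 0.01 per hour it is about 2%. The group-by-time interaction stays at 5% or below.

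**5. Secondary endpoint 6.** Sections 6.1 and 6.2 list a baseline endothelial test but no baseline heart scan, and the post-dose scan may be performed. The procedure description after the visit steps says the heart ultrasound will be performed. Section 3.1 says the post-dose set follows a protocol similar to baseline, and section 7.2 tabulates baseline values of secondary outcomes. These statements do not agree.

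**The case against.** A valid reading already exists. The t test may be paired, and with 30 pairs the claimed 80% power is met without a covariate (85.0% at ρ = 0 if 5% is the SD of one day's change). Baseline adjustment is then a gain in efficiency, not the repair of an error. That stands. What remains is that the plan does not commit to the paired form and makes drug a between factor for its key test.

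Several stronger readings are tempting, but the documents do not support them:

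- **False positives in the primary test.** A reader might infer an inflated error rate. That needs a negative correlation between a subject's two changes, for which the documents give neither a figure nor a reason. With positive correlation the test is conservative.
- **A large power gain on top of a faulty level.** The highest adjusted powers come from settings where the two changes are uncorrelated, which is where the unpaired test keeps its level. The two harms should not be added together.
- **A set power loss from one-day subjects.** Section 4.4.1 continues enrolment until the desired number is completed, so one-day subjects may be additional to 30 completers.
- **Endpoint 1 is likely to be falsely positive.** The size of the bias depends on assumed rates and window lengths. The placebo comparison and the interaction are free of it, because both days follow the same protocol.
- **Heart function cannot be analysed.** A post-dose scan is listed on both days, so an Adderall-placebo contrast is available, and section 3.1 may mean that the visit steps are incomplete.

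**Conclusion.** The point holds for the primary analysis. As written, drug as a between factor contradicts the crossover, and the choice of t test is left open. If a subject's two changes are positively correlated, the cost is a test that is too strict and lost power. At 0.5 SD the loss is 61−48 = 13 points at ρ = 0.3 and 76−47 = 29 points at ρ = 0.5. At the plan's own effect of 0.80 it is only about 5-6 points. At ρ = 0 there is essentially no cost. These figures assume normally distributed changes and 30 subjects, and every correlation is an assumption.

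Baseline adjustment is worth having because it is cheap. It lifts 80% power to about 82%-97% if the two changes are uncorrelated and about 81%-90% if they are correlated 0.2-0.5. The gain is small when same-day correlation is high.

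The secondary parts are matters of consistency. Endpoint 1 and Secondary Hypothesis 1 name different comparators, and the heart-ultrasound timing differs between sections. The plan should be corrected on all three points, but none prevents a valid analysis of the trial as designed.

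**What to change.** **Primary analysis.** In sections 7.1 and 7.2, remove drug as a between factor and remove the unpaired option. Specify a mixed model of post-dose BP and HR with drug, period and sequence as fixed effects and subject as random effect. Use the same visit's pre-dose value as covariate, split into the subject's mean and the visit's deviation from it. State that this is the two-day model meant under missing data; it also uses any one-day subjects. Keep the paired change test as a sensitivity analysis.

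**Secondary endpoint 1.** Reword it as Adderall against placebo over the same post-dose window. Use a paired binary method for incidence, such as exact McNemar. Report the discordant counts and a confidence interval, because power will be low: 5%-42% in simulation if the drug doubles an assumed rate of 0.02-0.2 per hour. Draw no inference from the before/after comparison within Adderall.

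**Secondary endpoint 6.** Reconcile the visit steps with section 3.1, the procedure description and section 7.2. If no pre-dose heart scan is done, define the cardiac part as the within-subject post-dose difference, Adderall minus placebo.

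**Cost.** Text changes, and one or two degrees of freedom for the covariate. No procedure is added and no subject is dropped from the BP and HR analysis. The heart-function contrast would rest on subjects scanned on both days.

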7.2 Statistical Methods

Descriptive Statistics

Univariate descriptive statistics and frequency distributions will be calculated, as appropriate for all variables. Baseline values for demographic, clinical, and outcome variables (primary and secondary) will be tabulated for both groups (i.e., study drug vs placebo drug). Data will be inspected before analysis for the need of transformations to reduce the possible impact of outliers in skewed distributions, and transformed accordingly. Distributions across subgroups used in randomization will also be compared to assess whether the randomization was successful in equalizing distributions of these prognostic variables across treatment groups. Putative prognostic variables that will be investigated through these descriptive analyses include variables such as BP, HR, age, gender, BMI, baroreflex sensitivity, catecholamine responses.

Handling of Missing Data

We expect missing data to be minimal. However, some subjects may drop out from the two study day protocol. The two-day longitudinal model is flexible to allow available data to be analyzed, for instance, if a subject completes the first study day, but not second study day. These models assume ignorable (MCAR/MAR) missingness. Sensitivity analyses may be performed to assess the robustness of these assumptions.

Multiplicity

There is no need to account for multiple comparisons in this study. With only 30 subjects, no correction for multiple comparisons using Bonferroni or Tukey's procedure will be necessary.

Primary Hypothesis: We hypothesize that BP and HR increase after intake of study drug compared to placebo.

Data will be analyzed using two-way analysis of variance (ANOVA) for repeated-measures with time (before vs after drug intake) as the within factor and group (study drug vs placebo drug) as the between factor. The key variable will be the group-by-time interaction. Differences in hemodynamics before and after consumption of a drug will be determined by repeated measures ANOVA. Student *t* test (paired or unpaired) will be used for between group comparisons with respect to change in given variable. $P < 0.05$ will be considered statistically significant. Data will be expressed as mean \pm SEM.

Secondary Hypothesis 1: We hypothesize that study drug will induce more frequent and more severe electrocardiographic findings compared to intake of a placebo drug. We hypothesize that biochemical/metabolic responses to consumption of study drug will be altered after consumption of study drug as compared to placebo drug (ie: increased catecholaminergic response after study drug consumption).

Data will be analyzed using two-way analysis of variance (ANOVA) for repeated-measures with time (before vs after drug intake) as the within factor and group (study drug vs placebo drug) as the between factor. The key variable will be the group-by-time interaction. Differences in electrocardiographic and biochemical/metabolic responses before and after consumption of a drug will be determined by repeated measures ANOVA. Student *t* test (paired or unpaired) will be used for between group comparisons with respect to change in given variable. $P < 0.05$ will be considered statistically significant. Data will be expressed as mean \pm SEM.

Interim Analysis

There will not be any interim analysis.

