4.4 Early Withdrawal of Subjects

4.4.1 When and How to Withdraw Subjects

Subject participation in this study is completely voluntary. Subjects can withdraw their consent and discontinue participation in the study at any time without affecting their relationship with Mayo Clinic doctors or Mayo Clinic. Although we do not anticipate high withdrawal rates in our healthy study population, rare possible reasons for withdrawal from this protocol is if subject becomes suddenly concerned about the safety or side effects of the study drug. This type of

withdrawal could be prevented by clear disclosure of the potential side effects of Adderall to the subject prior to enrollment. However if such situation does occur, subject will be allowed to discontinue participation in the two day study protocol.

Subject participation in this study may be ended by the principal investigator if it is felt it is in the best interest of the subject, if subjects do not follow the study procedures, or if the study is stopped.

Subjects will not need to be replaced per-se; enrollment of subjects will continue until desired number of participants is completed. There is no long term follow up in this study protocol.

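### The missing-data section claims validity under MAR from a longitudinal model that is never specified, and none of the analyses the plan names has that property

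*Combined protocol and SAP*

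**What the plan says.** Section 7.2 (Handling of Missing Data) expects few missing data but allows for dropout between the two study days. It states that "The two-day longitudinal model is flexible to allow available data to be analyzed", and gives as its example the case "if a subject completes the first study day, but not second study day". The assumption follows: "These models assume ignorable (MCAR/MAR) missingness". Checks on it are optional: "Sensitivity analyses may be performed to assess the robustness of these assumptions".

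The analyses themselves appear in section 7.1 (Data Analysis Plan) and again in section 7.2 under the primary hypothesis and secondary hypothesis 1. The first is a two-way repeated-measures ANOVA with "time (before vs after drug intake) as the within factor and group (study drug vs placebo drug) as the between factor", where the group-by-time interaction is the key term. The second is a Student t test ("paired or unpaired) will be used for between group comparisons with respect to change in given variable").

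Section 7.3 defines the population: "All-randomized population: Any subject randomized into the study". Section 4.4.2 allows data collected before withdrawal to be used. Section 4.4.1 gives, as a rare reason for withdrawal, "if subject becomes suddenly concerned about the safety or side effects of the study drug".

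**The concern.** The missing-data paragraph is the only place where a longitudinal model is mentioned. No fixed or random effects, covariance structure, estimation method, period or sequence term, or imputation is given anywhere. An analyst who follows the plan will therefore run the ANOVA or one of the two t tests, and the stated protection against ignorable dropout comes from none of them.

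Two things are at stake. First, the drug effect on BP and HR is biased if the decision not to return depends on what was seen on day 1. Section 8 lists raised BP and HR among the possible side effects, so such a link is plausible, though not established. Second, because the choice between paired and unpaired is left open, a later decision by the analyst would set the direction of that bias.

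**Working it through.** The plan gives no figure for missing data. From section 7.1 I take n = 30, a difference of 4% and an SD of 5%, hence an effect of 4/5 = 0.80 SD. The 80% power stated there is not reproduced by either test: 30 observations per treatment give 86% unpaired, and a standardised paired difference of 0.80 with n = 30 gives 98.8%. That is a separate matter, and nothing below depends on it. The dropout pattern and the within-subject correlation of changes (rho) are my assumptions.

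**Step 1: who stays in each analysis.** Take 30 subjects, 3 of them with day 1 only. That leaves 27 × 2 + 3 = 57 sessions.
- Paired t test: 27 pairs; the 3 subjects are lost.
- ANOVA as written (drug between): all 57 sessions are kept. In a test dataset its interaction F was 17.39 on 55 df, equal to the square of the unpaired t on change. The two are the same test.
- ANOVA with drug also as a within factor: the standard routine rejects the data as unbalanced, so the 3 subjects would have to be removed. The plan does not specify this version.

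**Step 2: bias in an assumed worst case.** Blocks of 6 with 30 subjects imply 15 per sequence. Suppose the k largest day-1 changes among the 15 Adderall-first subjects belong to those who do not return. Let S be the sum of the k largest expected values of 15 standard normal draws (1.736, 1.248, 0.948). Then S = 2.984 for k = 2 and 3.932 for k = 3.

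The 15 - k Adderall-first subjects who remain have a mean Adderall change shifted by -S/(15 - k) SD, and a mean placebo change shifted by rho times that.
- Complete pairs: bias = -(1 - rho) × S/(30 - k).
- Unpaired, or ANOVA as written: the Adderall mean uses all 30 subjects and is unbiased. The placebo mean is too low, so bias = +rho × S/(30 - k).

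S/(30 - k) is 2.984/28 = 0.107 for k = 2 and 3.932/27 = 0.146 for k = 3.

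| rho | k | Complete pairs (SD) | Unpaired / ANOVA as written (SD) |
|---|---|---|---|
| 0.3 | 2 | -0.075 | +0.032 |
| 0.3 | 3 | -0.102 | +0.044 |
| 0.5 | 2 | -0.053 | +0.053 |
| 0.5 | 3 | -0.073 | +0.073 |

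Simulation (1,500 trials per cell) agrees with these values within its error. A REML model with drug, period, sequence and a subject random effect, fitted to the same data, was within about 0.01 SD of the truth in every cell.

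**Step 3: a smoother dropout rule.** Let the chance of missing day 2 rise with the day-1 change, with 8% to 24% lost and rho from 0.3 to 0.7 (200,000 simulated subjects, true difference 4.0). Complete pairs give 3.72 to 3.91, the unpaired analysis 4.07 to 4.28, and a likelihood analysis of all available data 3.99. The first two are off by about 2% to 7% of the effect, in opposite directions.

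**Step 4: no dropout at all.** The unpaired analysis estimates the variance of the difference as 2 × SD²/n, while the true value is 2 × SD² × (1 - rho)/n. The two-sided type I error is then roughly 2 × [1 - Phi(1.96/√(1 - rho))], that is 1.9%, 0.6% and 0.03% at rho 0.3, 0.5 and 0.7. Simulation with the t reference (20,000 trials) gives 2.3%, 0.75% and 0.09%, against a nominal 5%.

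**The case against.** The strongest reply is that the sponsor may mean a likelihood mixed model by a longitudinal model. If so, the MAR statement would be right. But for the primary hypothesis the plan names other methods, and a reader cannot take an unnamed model to override them.

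A second reply is that little dropout is expected. This stands as a limit on size. Section 7.2 expects minimal missing data, and section 4.4.1 calls withdrawal over side-effect concern rare and preventable by disclosure before enrolment. That section describes concern rather than an experienced reaction, and does not tie it to the Adderall day. Losing exactly the strongest responders is my worst case, not the protocol's expectation.

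Three stronger readings are tempting, and the documents do not support them:
- A reader might infer that the repeated-measures ANOVA discards one-day completers. As written, with drug between, it keeps them, as does the unpaired t test. The conflict with the all-randomised population therefore arises only for the paired test.
- A reader might infer that the bias is always towards zero. That is true only of complete pairs.
- A reader might infer a power loss from 80% to 75% when 30 pairs become 27. Those figures rest on a 0.53 SD effect that is not in the documents. Section 4.4.1 also continues enrolment until the desired number is completed, which can restore the count, though it does not remove selection.

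**Conclusion.** Wrong as written, with modest impact. The claim of validity under MAR is attached to a model the plan does not contain, and no analysis it does contain supports the claim. The paired test fails because it discards day-1 data; the between-group analyses fail because they ignore the link between a subject's two days.

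In the assumed worst case the bias is at most about 0.10 SD. That is 0.10/0.80, or about 13% of the planned effect, and 0.10 × 5 = 0.5 percentage points on the plan's 4-point difference. Under the smoother rule it is 2% to 7%. With no dropout the bias vanishes. What then remains is the conservatism of the between-factor analysis, with type I error of about 2% at correlation 0.3, under 1% at 0.5 and about 0.1% at 0.7. These sizes depend on assumed correlations and dropout patterns. The mismatch between the claim and the named analyses does not.

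**What to change.** In sections 7.1 and 7.2, and in the Study Summary's statistical methodology entry, replace the between-factor ANOVA and the open choice of t test with one primary analysis. This should be a linear mixed model fitted by REML to each session's change in BP and in HR, with drug, period and sequence as fixed effects and subject as a random effect, using all available days of all randomised subjects. Use the same model for the continuous outcomes under secondary hypothesis 1.

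In the missing-data paragraph, refer to this model by name and state that its validity under MAR comes from likelihood estimation on all available days. Make the sensitivity analysis mandatory, and pre-specify the complete-pairs paired t test for it.

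The cost is a change of wording before unblinding. No extra subjects, visits or measurements are needed.
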